## **5.4 Demographic and Other Baseline Characteristics**

### **5.4.1 Demographic Characteristics**

All demographic and baseline characteristics will be summarized by cohort for both SS and PK populations and listed accordingly. The summary will include age, gender, race, height, baseline bodyweight, baseline BMI and screening and baseline ECOG. If two populations are identical, the table will be appropriately identified as representing both populations and will not be duplicated. Demographic characteristics will be also provided by subtype of cancer (solid tumours except T-ALL/T-LBL, Adenoid Cystic Carcinoma, T-ALL or T-LBL).

Patients' initial cancer history will be summarized, including tumour type (for breast cancer including ER, PR and HER2 status), Notch status as well as histological tumour grade of initial cancer, also whether or not previous systemic anti-cancer treatments, previous radiotherapies or previous surgeries had been applied and if cancer is recurrent or metastatic; the full information on primary cancer will be provided in Listings.

Active medical history (i.e. histories marked as ongoing at time of screening) will be summarized by number of active disease events, number and percentage of patients with at least one active

disease and number and percentage of patients with each disease displayed by System Organ Class (SOC) and preferred term (PT).

Prior systemic anti-cancer (AC) therapies will be summarized by number and percentage of patients previously treated with at least one systemic agent, by line of prior therapy, best response to and reason for discontinuation of prior therapy as well as number and percentage of patients who progressed under the prior therapy. These will also be summarized by number of systemic therapies, number and percentage of patients previously treated with at least one systemic agent and number and percentage of patients treated with each systemic agent displayed by type of cancer and preferred drug name and listed. Prior radiotherapy will be summarized by number and percentage of patients who received any prior radiotherapy, by body location of, setting of and best response to prior radiotherapy as well as number and percentage of patients who progressed after prior radiotherapy. Prior surgery will be summarized by number and percentage of patients with any prior surgery, by type, body location and outcome of prior surgery as well as number and percentage of patients who progressed after prior surgery.

Substance use at screening will be summarized for smoking status, alcohol use and drug abuse.

Vital signs and ECOG status at baseline will be summarized and listed.

Physical examination at baseline will be listed.

Fresh tumour biopsies collected at baseline will be listed only.

**Notes:**

- Age will be derived in eCRF from entered year of birth.
- Medical history will be coded according to MedDRA version will be noted in the footnote of the Tables.
- Active medical history is defined as marked as ongoing at time of screening.
- Prior systemic AC therapies will be coded according to WHO-Drug Dictionary version will be noted in the footnote of the Tables.

**5.4.2 Prior and Concomitant Medications**

Incidence of prior and concomitant medication will be presented by cohort, ATC class and preferred drug name and listed.

Prior medications are those that started and stopped before exposure to study medication; concomitant medications are all medications taken during the study period, including those started before but on going at first dose.

Where a medication start date is partially or fully missing, and it is unclear as to whether the medication is prior or concomitant, it will be assumed that it is concomitant.

Medications within 24 hours prior to PK sampling will be listed only.

**Note:**

Medications are coded using WHO Drug dictionary version will be stated in the footnote of the tables.

## 5.5 Measurements of Treatment Compliance and Exposure

Exposure to study drug will be summarized overall and by cohort as well as by cycle for the SS for following parameters:

- Cumulative dose (in g)
- Duration of study treatment (in months)
- Actual exposure (in months)
- Actual dose intensity (in mg/d)
- Planned dose intensity (in mg/d)
- Relative dose intensity (in %)
- Treatment compliance (in %)

All information recorded concerning study drug modifications will be listed.

### Notes:

Duration of study treatment (months) is defined as:

$$(\text{date of last dose of study treatment} - \text{date of first dose} + 1) / 30.4375.$$

Actual exposure (months) is defined as:

$$\text{number of days when patients actually took study medication} / 30.4375.$$

Actual dose intensity (mg/d) is defined as:

$$\text{total actual dose taken (mg)} / \text{actual exposure (d)}.$$

Planned dose intensity (mg/d) is defined as:

$$\text{total planned dose taken (mg)} / \text{planned exposure, i.e. planned days on treatment (d)}$$

Relative dose intensity is defined as:

$$\text{actual dose intensity} / \text{planned dose intensity} \times 100\%$$

Treatment compliance (in %) is defined as:

$$\text{total actual dose taken} / \text{total planned dose} * 100$$

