### **10.3 STUDY TREATMENT**

The actual dose received and the duration of CB-103 as well as the dose intensity (actual dose received/actual duration) will be listed and summarised by cycle and overall using descriptive statistics.

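### On once-daily dosing, the SAP's relative dose intensity does not register whole days without drug, because its denominator counts only days on which drug was taken

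*SAP*

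**What the plan says.** The notes to SAP 5.5 (Measurements of Treatment Compliance and Exposure) define the measures as follows.

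- Actual exposure is the "number of days when patients actually took study medication", converted to months for display.
- Actual dose intensity is "total actual dose taken (mg") divided by "actual exposure (d").
- Planned dose intensity is the total planned dose divided by "planned exposure, i.e. planned days on treatment (d").
- RDI is actual over planned dose intensity, as a percentage.
- Treatment compliance is total dose taken over total planned dose, as a percentage.
- Duration of study treatment is a calendar span: the "date of last dose of study treatment" minus the first-dose date, plus one. It is tabulated but does not enter RDI.

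All of these are to be summarised overall, by cohort and by cycle on the safety set.

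Protocol 10.3 lists "the dose intensity (actual dose received/actual duration") and does not say what actual duration means. SAP section 6 states that nothing has changed from the analysis planned in the protocol.

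**The concern.** A dose-intensity measure is normally read as drug delivered per unit of time on treatment. Here the clock stops on every day without drug. That matters because withholding drug is a common response to toxicity in the Protocol 7.4.6.1 tables, and several of their rules resume at the same dose afterwards (for example, short-lived Grade 3 neutropenia or transaminase elevation, and Grade 2 visual symptoms). Under Protocol 7.4.5 held or missed doses are not made up. If such a hold is a patient's only modification, RDI stays at 100%.

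Protocol 9.2.1 lists drug exposure, with dose intensities and modifications, among the ways safety is evaluated. A reader who takes RDI from the report without the neighbouring lines would overstate the dose delivered.

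**Working it through.** The SAP gives no worked exposure figure, so there is nothing to reproduce. The check applies its definitions directly.

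**Inputs.** Continuous once-daily dosing and a 28-day cycle (SAP 2.1.2). The illustrative dose is 600 mg (Protocol 2.5.6); any other dose cancels out of RDI.

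**General form.** Let D be the planned daily dose, n the planned days, k the days on which the full dose was taken, and L the days from first to last dose inclusive.

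- Actual dose intensity (SAP) = kD / k = D
- Planned dose intensity = nD / n = D
- RDI (SAP) = D / D = 100% for every k of at least 1
- Compliance = kD / nD = k / n
- RDI with duration as denominator = (kD / L) / D = k / L

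**Numbers for 7 days on, 14 off, 7 on.** Total taken is 14 × 600 = 8,400 mg; planned is 28 × 600 = 16,800 mg.

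- SAP: 8,400 / 14 = 600 mg/d; 16,800 / 28 = 600 mg/d; RDI 100%
- Compliance: 8,400 / 16,800 = 50%
- With duration: 8,400 / 28 = 300 mg/d; RDI 50%

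**Other patterns over 28 planned days at 600 mg.**

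| Pattern | Total mg | Days taken | Span L | RDI (SAP) | Compliance | RDI on span | RDI on 28 days |
|---|---|---|---|---|---|---|---|
| Every day | 16,800 | 28 | 28 | 100% | 100% | 100% | 100% |
| 7 on, 14 off, 7 on | 8,400 | 14 | 28 | 100% | 50% | 50% | 50% |
| Alternate days | 8,400 | 14 | 27 | 100% | 50% | 51.9% | 50% |
| 10 on, 7 off, 11 on | 12,600 | 21 | 28 | 100% | 75% | 75% | 75% |
| First 14 days only | 8,400 | 14 | 14 | 100% | 50% | 100% | 50% |
| Half dose every day | 8,400 | 28 | 28 | 50% | 50% | 50% | 50% |

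Two things follow. The SAP's RDI responds to a lower dose on days taken (last row) but not to days without drug (rows 2 to 5). And the first-to-last-dose span recovers gaps only when they lie inside the span. If the drug is withheld for days 15 to 28 of a cycle and then restarted, a span computed within that cycle still gives 8,400 / 14 = 600 mg/d and RDI 100%. Counting the days in the cycle gives 8,400 / 28 = 300 mg/d and RDI 50%.

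**The case against.** **The shortfall is already reported.** This stands. Compliance shows 50% for the example patient, duration sits beside actual exposure in the same summary, all drug modifications are listed, and adverse events leading to interruption are summarised under SAP 5.7.1. Every formula is printed. What remains is that RDI of 100% beside compliance of 50% invites misquotation, and the SAP does not say what each is for.

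**The protocol is not clearly contradicted.** A reader might infer that the SAP breaches Protocol 10.3. The text does not establish that, because actual duration is undefined there. Elapsed time is the more natural reading, since the SAP itself treats duration and actual exposure as separate quantities. The supportable statement is that the two wordings are unaligned and section 6 does not mention it.

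**RDI does not drive the dose decision.** A reader might infer that confirmation of the recommended dose rests on RDI. The documents do not support this. The confirmatory-cohort primary endpoint (Protocol 4.2.1, SAP 2.5) is built on drug reactions, laboratory, vital signs, ECG and cardiac imaging. The committee review in Protocol 10.8.1 names Grade 3 or higher events, serious events, laboratory abnormalities and available safety data. SAP 5.7 does not list dose intensity, and no rule uses it.

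**RDI is not blind to every missed dose.** On a twice-daily schedule, missing one of two doses each day keeps all 28 days in the denominator, so RDI falls to 50%. The insensitivity is to whole days without drug.

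**The example is near an extreme.** Protocol 7.4.5 generally ends participation after more than 14 days of continuous interruption, so the 14-day gap sits at that limit. In Cycle 1, patients without a DLT need at least 21 dosing days to enter the dose-determining set (SAP 3.2), so for them missed days can open a gap of at most 100% − 21/28 = 25 percentage points between RDI and compliance. The exposure tables use the safety set, which has no such minimum.

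**Conclusion.** The definition gives a misleading value and should be changed. On once-daily dosing, any pattern of whole days without drug, with full doses on the remaining days, yields RDI of exactly 100%, against 50% compliance in the 14-of-28-day example and 75% for 21 of 28 days. This assumes full doses on days taken; the 50% duration-based RDI for the example also assumes that the gap lies between the first and last dose.

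The consequence is limited to actual and relative dose intensity as descriptive exposure summaries. The DLT analysis and the dose-toxicity model do not use them.

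**What to change.** In SAP 5.5:

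1. Define overall actual dose intensity as total actual dose divided by duration of study treatment in days (last-dose date minus first-dose date plus one, interruptions included).
2. For by-cycle summaries, use days in the cycle up to permanent discontinuation, so that omissions at the end of a cycle count. Since Protocol 7.4.5 lets an interruption run past day 28 before the next cycle begins, say which cycle those extra days belong to.
3. Keep days actually dosed as a separate line.
4. State that RDI measures intensity while on treatment and compliance measures total dose against plan. The two then differ for a patient who stops early: stopping permanently after day 14 of 28 gives RDI 100% and compliance 50%, each correct for its purpose. Using planned days as the RDI denominator would instead make RDI identical to compliance.

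If the sponsor prefers the present measure, it should be labelled as mean dose per dosing day, with the difference from Protocol 10.3 noted in SAP section 6.

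The cost is one SAP definition with its by-cycle variant, using data already needed for the planned exposure tables. Some reported RDI values become lower.

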## 5.6 Primary Analysis

### 5.6.1 Dose Escalation

Each dose escalation step is considered an IA.

An adaptive BLRM guided by the EWOC principle will be used in the dose escalation.

The BLRM will be updated with the respective number of patients treated and the number of DLTs observed in the last cohort. The updated model will then give a statistical recommendation for the next escalation step. However, a risk-benefit assessment that includes a comprehensive analysis of safety and available clinical information will be done to decide on the next escalation steps.

#### 5.6.1.1 Dose-Finding of Single Agent CB-103

A 2-parameter BLRM (Neuenschwander et al 2008) will be used for dose escalation. Standardised doses will be used such that one of the doses ( $d^*$ ) equals 1, e.g., doses are rescaled as  $d/d^*$ . As a consequence,  $\alpha$  is equal to the odds of the probability of toxicity at  $d^*$ . All information currently available about the dose-DLT relationship of CB-103 is summarised in a prior distribution. For this study, this includes pre-clinical data about the starting dose and predicted MTD of CB-103 within different animal species. This prior distribution is then updated after each cohort of patients with all the DLT data available in the DDS from the current trial. Once updated, the distribution summarises the probability that the true rate of DLT for each dose lies in the following categories:

- [0,16%] under-dosing
- [16%,33%] targeted toxicity
- [33%,100%] excessive toxicity

The EWOC principle (Babb et al 1998, Neuenschwander, et al 2008) mandates that any dose of CB-103 that has more than a 25% chance of being in the excessive toxicity category is not considered for the next dose cohort.

In case that another regimen is evaluated during the study, a separate 2-parameter logistic regression will be used for the assessment of the respective DLT rates. However, all data that are available from the other regimen (or regimens) before “First Patient First Visit” (FPFV) for the new regimen has happened will be incorporated into an informative, meta-analytic predictive (Neuenschwander et al 2015) prior distribution. This prior distribution will be mixed with a weakly informative prior distribution to hedge against a potential prior-data conflict.

The frequency of DLTs will be tabulated by dose for patients in the dose escalation phase and information about the DLTs will be listed by dose.

#### 5.6.1.2 Bayesian Logistic Regression Model to Determination of MTD

The objective of the design is to determine the MTD defined as the highest dose with less than 25% risk of the true DLT rate being above 33%. The Part A dose-finding will be guided by a Bayesian 2-parameter logistic regression model with overdose control.

The model is formulated as follows:

$$\text{logit}(p(d)) = \log(\alpha) + \beta \cdot \log(d/d^*)$$

where  $\text{logit}(p) = \log(p/(1-p))$ .

$p(d)$  represents the probability of having a DLT in the first cycle at dose  $d$ ,  $d^* = 150$  mg is the reference dose, allowing for the interpretation of  $\alpha$  as the odds of a DLT at dose  $d^*$ , and  $\theta = (\log(\alpha), \log(\beta))$  with  $\alpha, \beta > 0$  is the parameter vector of the model.

Since a Bayesian approach is applied, a prior distribution  $\pi(\theta)$  for the unknown parameter vector  $\theta$  needs to be specified. This prior distribution will be specified as a mixture of two multivariate normal distribution, i.e.

$$\pi(\theta) = \varphi_1\pi_1(\theta) + \varphi_2\pi_2(\theta)$$

with  $\varphi_i$ ,  $i = 1, 2$  the prior mixture weights ( $\varphi_1 + \varphi_2 = 1$ ) and  $\pi_i(\theta) = \text{MVN}(\mu_i, \Sigma_i)$  the multivariate normal distribution of the  $i$ -th component with mean vector  $\mu_i$  and covariance matrix  $\Sigma_i$ , with

$$\Sigma_i = \begin{pmatrix} \sigma_{i,11}^2 & \sigma_{i,11}\sigma_{i,22}\rho_i \\ \sigma_{i,11}\sigma_{i,22}\rho_i & \sigma_{i,22}^2 \end{pmatrix}$$

Mixture prior distributions have the advantage that they allow for specification of different logistic dose-toxicity curves, therefore making the prior more robust.

### Prior derivation

For the current study, data from the pre-clinical animal studies were available. Therefore, the following prior will be used: A combination of the observed toxicity data from a study in rats further supported by data from a study in dogs.

#### Prior from rat data:

Based on the IMPD, the starting dose of CB-103 will be 15 mg, which is expected to achieve an exposure ( $\text{AUC}_{0-24}$ ) in humans of approximately  $600 \mu\text{g}\cdot\text{h}/\text{mL}$ . This exposure is comparable with 1/10th of the exposure at the highest non-severely toxic dose (HNSTD) (30 mg/kg/day) in male rats. It is therefore highly unlikely that a DLT would occur at this dose, leading to the prior assumption that the median DLT rate at 15mg is 0.1%. On the other hand, assuming dose-proportionality in humans, a dose of 150 mg would approximately have an exposure of  $6000 \mu\text{g}\cdot\text{h}/\text{mL}$ , i.e., the same as the exposure at the HNSTD in rats. Using a cautious approach, the median DLT rate at  $d^* = 150$  mg was therefore assumed 25%.

#### Prior from dog data:

Based on the IMPD, the exposure at 1/10th of the HNSTD (8.6 mg/kg/day) in (male) dogs is approximately  $9000 \mu\text{g}\cdot\text{h}/\text{mL}$ , which we would correspond to a human dose of  $15 \cdot 9000 / 600 = 225$  mg, with a prior median DLT rate of 0.1%. A cautious approach was chosen again, using a median 25% DLT rate at  $d = 225$  mg.

**Table 4 Summary of prior distribution**

Prior Component	Mixture Weight	Mean vector	SD vector	Correlation
1: Rat	0.500	-1.122, 0.299	1.98476, 0.9906	-0.0004715777
2: Dog	0.500	-1.682, -0.101	1.9847620, 0.9906	-0.0004715777

A summary of the prior probabilities of DLT at different doses, as well as the corresponding probability of under-, targeted and overdosing, are shown in Table 5. The prior medians of the DLT probabilities are in line with the prior medians derived from the two animal studies, and the uncertainty around the medians is large, showing the low amount of in-men information this prior provides.

**Table 5 Prior probabilities of DLT at selected doses**

Dose	Probability of true DLT rate in			Mean	SD	Quantiles		
	[0–0.16)	[0.16–0.33)	[0.33–1]			2.5%	50%	97.5%
10 mg	0.857	0.069	0.075	0.077	0.162	0	0.008	0.647
15 mg	0.832	0.079	0.089	0.089	0.173	0	0.012	0.685
30 mg	0.775	0.101	0.123	0.118	0.197	0	0.025	0.757
60 mg	0.688	0.129	0.182	0.165	0.228	0	0.057	0.828
120 mg	0.524	0.178	0.298	0.253	0.266	0.003	0.144	0.898
180 mg	0.384	0.186	0.429	0.347	0.3	0.006	0.256	0.954
240 mg	0.31	0.171	0.519	0.418	0.324	0.008	0.352	0.986
320 mg	0.26	0.153	0.588	0.479	0.339	0.011	0.449	0.998
400 mg	0.229	0.141	0.63	0.52	0.345	0.013	0.525	0.999

Doses printed in bold type meet the overdose criterion,  $P(\text{overdose}) < 0.25$ .

The MTD may be considered reached if one of the following criteria is fulfilled:

1. The posterior probability of the true DLT rate in the target interval (16%-33%) of the MTD is above 50%

OR

2. At least 6 patients have been treated at MTD, including the confirmatory cohort.

**Statistical model assessment**

The single agent model was assessed using two different metrics:

1. Hypothetical data scenarios: for various potential data constellations as they could occur in the actual trial, the maximal next doses as allowed by the model and by the 100% escalation limit are investigated. Data scenarios thus provide a way to assess the “on-study” behaviour of the model.

2. Simulated operating characteristics: these illustrate for different assumed true dose-toxicity relationships, how often a correct dose would be declared as MTD by the model. They are a way to assess the “long-run” behaviour of the model.

In summary, the model showed very good behaviour as assessed by these metrics.

More details of the model for Part A can be found in Appendix 2.

### 5.6.2 Efficacy Analysis

All efficacy endpoints will be summarized within cohort by descriptive statistics based on SS.

Tumour assessments (via CT, MRI or PET-CT, bone marrow, respectively, pending on tumour type) are scheduled for following time-points:

- At baseline
- During Cycle 2, 4, 6, etc.: on Day 15 (i.e. every 8 weeks)
- At EOT visit

Progression-free Survival (PFS) is assessed explicitly at week 24 and at EOT visit, though disease progression can be detected and recorded at any time-point.

Efficacy parameters are:

- Overall Response Rate (ORR)
- Best Overall Response (BOR)
- Time to Response (TTR)
- Duration of Response (DOR)
- Clinical Benefit Rate (CBR) at 3 months, at 6 months and at 9 months
- Progression-free Survival (PFS)
- Overall Survival (OS)

No formal hypothesis testing is planned.

All lesion and other tumour assessments will be included in the assessment of efficacy parameters.

All efficacy parameters from either the eCRF or calculated as part of statistical analysis will be listed.

In case of patients with solid tumour cancers, baseline lesion status as well as post-baseline assessments of target, non-target and new lesions will be provided. The overall response assessment as of RECIST1.1 are listed by individual cycles.

In T-ALL/T-LBL patients, baseline lesion status, tissue sites involved at baseline, post-baseline lesion status and new lesions will be listed; and so will the overall response assessments by cycle based on NCCN Guidelines on Adult Acute Lymphoblastic Leukaemia.

Patients who cannot be evaluated for response will be categorized as Not Evaluable (NE) or Unknown/Not Assessed (NA).

### 5.6.2.1 Best Overall Response (BOR)

BOR is defined as the best response recorded from the first day of study treatment until disease progression/recurrence, death or end of study respectively data cut-off, whatever comes first.

Patients with solid tumours are considered responders if they have a tumour assessment status of PR or CR according to RECIST, v1.1.

The best overall response is the best response recorded from the start of the treatment until disease progression/recurrence. Best is defined as the first response when all a subject's response assessments are sorted by CR, PR, SD, PD, NE/UNK. In general, the subject's best response assignment will depend on the achievement of the measurement criteria. For subjects without a post-baseline, a non-missing response assessment will have a BOR of NE assigned. Unknown (UNK) or patients with symptomatic deterioration but without any scan will also be mapped to NE.

Patients with haematologic malignancies are considered responders if they have a haematologic malignancies status CR or CRi as per NCCN guidelines.

Any response must be confirmed not less than 4 weeks after the criteria for response are first met.

Patients without a post-baseline assessment will be considered NE. Additionally, after baseline, a change in methods will result in an assessment of not evaluable.

Patients who were enrolled in study, but did not receive any study treatment will have a best overall response 'Missing' and will be included as non-responders in the analysis of BOR.

BOR for different cancer types will be summarized by cohort for patients with Solid Tumour and for those with haematologic malignancies. The BOR information will be provided in Listing.

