### **Treatment period**

Solid tumours (six-twelve cycles): the treatment period commences on the first day of the first cycle of CB-103 treatment (1st administration of CB-103) and ends on the last day of dosing (within the 6 cycles period for Part A or 12 cycles period for Part B).

T-ALL/T-LBL: initial treatment with CB-103 single agent is given for 28 days (one cycle). Patients are assessed for disease response on day 29 ( $\pm 3$  days); however, if the day 29 marrow is hypocellular (cellularity  $\leq 15\%$ ), then treatment with CB-103 may continue and a repeat bone marrow biopsy is obtained one week later (day 36) to assess response.

Patients achieving a CR are eligible to receive 2 additional courses of CB-103 as consolidation therapy at the same dose and schedule as outlined above. Treatment may be discontinued if the patient is scheduled for HCT, otherwise additional courses of CB-103 until relapse may be given after discussion with the Sponsor.

If residual leukaemia/lymphoma is documented at the point of marrow recovery (cellularity  $\geq 15\%$ ) after the first induction cycle, then a second course of CB-103 is administered.

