### **Evaluation of best overall response**

The best overall response is the best response recorded from the start of study treatment until the EOT taking into account any requirement for confirmation. A response occurring after the end of study treatment but prior to the start of a new cancer treatment will also be considered for the assessment of best overall response. This assessment should be performed as per clinical standard practice. When a response assessment according to RECIST 1.1 is available, the result should be recorded in the eCRF. If no results of response assessment according to RECIST are available, then the result of other tumour evaluation should be recorded in the eCRF including the method used.

**Table 1** Overall Response assessment for patients with target and non-target lesions at a given timepoint

Target lesions	Non-target lesions	New lesions	Overall response
CR	CR	No	CR
CR	Non-CR/Non-PD	No	PR
CR	Not evaluated	No	PR
PR	Non-PD or not all evaluated	No	PR
SD	Non-PD or not all evaluated	No	SD
Not all evaluated	Non-PD	No	NE
PD	Any	Yes or No	PD
Any	PD	Yes or No	PD
Any	Any	Yes	PD

CR = complete response; NE = not evaluable; PD = progressive disease; PR = partial response; SD = stable disease

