## **Appendix 8 Response Assessment in Acute Lymphoblastic Leukaemia/ Lymphoblastic Lymphoma**

### **Response criteria for Blood and Bone Marrow:**

- CR
  - No circulating lymphoblasts or extramedullary disease
  - No lymphadenopathy, splenomegaly, skin/gum infiltration/testicular mass/CNS involvement
  - Trilineage haematopoiesis (TLH) and <5% blasts
  - Absolute neutrophil count (ANC) >1000/microL
  - Platelets >100,000/microL
  - No recurrence for 4 weeks
- CR with incomplete blood count recovery (CRi)
  - Meets all criteria for CR except platelet count or ANC
- Overall response rate (ORR = CR + CRi)
- **NOTE:** MRD assessment is not included in morphologic assessment and should be obtained
- Refractory disease
  - Failure to achieve CR at the end of induction
- Progressive disease (PD)
  - Increase of at least 25% in the absolute number of circulating or bone marrow blasts or development of extramedullary disease
- Relapsed disease
  - Reappearance of blasts in the blood or bone marrow (>5%) or in any extramedullary site after a CR

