-  Bone marrow biopsy and/or aspirate (T-ALL/T-LBL): a bone marrow biopsy and/or aspirate will be obtained to assess bone marrow cellularity and to determine the percentage of leukemic blasts, including assessment of minimal residual disease (MRD) to confirm remission status. At the baseline assessment, bone marrow biopsy and/or aspirate is within 2 weeks and no less than 1 day before the first dose of CB-103. Then patients are assessed for disease response by bone marrow biopsy and/or aspirate on day 29. If the blasts in bone marrow are  $<5\%$  but marrow is hypocellular (cellularity  $\leq 15\%$ ) on day 29 ( $\pm 3$  days), then a repeat bone marrow biopsy and/or aspirate is obtained 1 week later to assess response; if residual leukaemia is present, repeated bone marrow biopsy and/or aspirate will be obtained per 28 days until CR or CRi. A response (CR or CRi) must be confirmed no less than 28 days from the first evidence of response by bone marrow core biopsy as indicated. In case of CR or CRi confirmed by bone marrow biopsy and/or aspirate on 2 bone marrow biopsy and/or aspirate assessments no less than 28 days apart (the interval between assessments), bone marrow biopsy and/or aspirate assessment may be increased to every 8 weeks until to PD or EOS (whichever is earlier).
-  Lumbar puncture (T-ALL/T-LBL) for prophylactic intrathecal therapy: if prophylactic intrathecal therapy is foreseen by the treating physician, a lumbar puncture may be performed up to 3 days before the first dose of CB-103, and, depending on the response of the patient, may be repeated at the discretion of the treating physician at the end of the first cycle of treatment with CB-103, and at the end of any subsequent cycle of treatment with CB-103, if more than one is warranted.
-  CSF sample (T-ALL/T-LBL): in patients in whom a lumbar puncture is done (e.g., for intrathecal prophylaxis) a CSF sample should be taken on or around cycle 1 day 28, if clinically feasible, to determine the exposure of CB-103 in the CSF.

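### For solid tumours the SAP's best overall response window omits the protocol's stop at new cancer treatment; for T-ALL/T-LBL neither document sets one

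*SAP*

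**What the plan says.** **SAP.** Section 5.6.2.1 counts the best response from the first day of treatment "until disease progression/recurrence, death or end of study respectively data cut-off, whatever comes first". A second sentence in the same section names only progression or recurrence as the end. Neither sentence mentions new anticancer therapy or transplant. Section 5.6.2 adds: "All lesion and other tumour assessments will be included in the assessment of efficacy parameters". On confirmation, 5.6.2.1 says: "Any response must be confirmed not less than 4 weeks after the criteria for response are first met". It does not require the confirming assessment to come before any later therapy.

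**Protocol, solid tumours.** Appendix 7 (Evaluation of best overall response) defines BOR as the "best response recorded from the start of study treatment until the EOT taking into account any requirement for confirmation". It then extends the window conditionally: "A response occurring after the end of study treatment but prior to the start of a new cancer treatment will also be considered".

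**Protocol, T-ALL/T-LBL.** Appendix 8 lists response categories but gives no BOR window and no stop at new therapy or transplant. Section 5.1.1.1 (Treatment period) offers patients in CR two further courses of CB-103 and adds: "Treatment may be discontinued if the patient is scheduled for HCT".

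**Declared changes.** SAP section 6 states that nothing in the protocol's planned analysis was altered.

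**The concern.** In a single-arm study, the response rate is read as activity of the study drug. That reading fails if the window stays open after the patient has moved to another treatment. The protocol closes this gap for solid tumours; the SAP reopens it without saying so.

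The patients exposed are those who leave CB-103 without progression, for example because of toxicity or a planned transplant. Patients who progress are already cut off under both rules. Any error runs in one direction, towards a higher BOR and overall response rate (ORR).

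**Working it through.** No figure in the plan depends on the window, so there is nothing to reproduce. The check compares the two texts, works through the timing, and then illustrates the size.

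**1. Closing events compared**

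| Event | Protocol Appendix 7 (solid) | SAP 5.6.2.1 | Protocol Appendix 8 (T-ALL/T-LBL) |
|---|---|---|---|
| Progression/recurrence | not named as the end of the window | closes | no window given |
| End of treatment | closes, with a conditional extension | does not close | no window given |
| New cancer treatment | closes the extension | not mentioned | not mentioned |
| Transplant | not named separately | not mentioned | not mentioned |
| End of study / data cut-off | not named | closes | no window given |

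For solid tumours the SAP drops a stated protocol limit. For T-ALL/T-LBL there is no protocol limit to drop; the rule is absent from both documents.

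**2. Timing if end of study is the patient's own visit.** Protocol 5.1.1.1 (Safety follow-up period) places this 28 days after the last dose. Let L be the day of the last dose, so the window closes at L + 28. Let new therapy start on day N, with N > L. Assume the confirming assessment must also lie inside the window, which the SAP does not state.

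- *Response first seen on the later therapy*, on day R ≥ N > L. Confirmation comes no earlier than R + 28, which exceeds L + 28. It falls outside the window and is not counted.
- *Response first seen on CB-103*, on day R ≤ L. Confirmation can come from R + 28, which is at most L + 28. It can lie inside the window and still fall after N.

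So on this reading only confirmation is exposed.

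**3. Timing if it means overall end of study or data cut-off.** The window stays open after L + 28. Both a first response and its confirmation on later therapy can then count. Protocol Appendix 7 provides for recording responses after treatment, and the tumour-assessment note to the SAP's Appendix 3 schedule runs scans to EOT or to progression/survival. Post-treatment assessments can therefore exist.

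**4. T-ALL/T-LBL.** The first response marrow is on day 29 (±3), and confirmation needs at least 28 more days: 29 + 28 = day 57. If CB-103 stops after cycle 1 (day 28) for transplant, the confirming marrow comes after stopping and may come after transplant. The patient-level end of study would be 28 + 28 = day 56. Confirmation on day 57 misses it by one day, while a first marrow on day 26 could be confirmed on day 54, inside it. The outcome therefore turns on which end of study is meant. Refractory disease ("Failure to achieve CR at the end of induction") is also a category separate from PD in Appendix 8, so a refractory patient who moves to other therapy does not clearly close the SAP window.

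**5. Size, illustration only.** Assume one response is counted in error. The intervals are exact Clopper-Pearson 95%, the method in SAP 5.6.2.2. The smallest dose group given an interval has 6 patients, and the confirmatory cohort has about 45.

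| n | 0 responders | 1 responder | Shift |
|---|---|---|---|
| 6 | 0% (0 to 45.9) | 16.7% (0.4 to 64.1) | 1/6 = 16.7 points |
| 45 | 0% (0 to 7.9) | 2.2% (0.1 to 11.8) | 1/45 = 2.2 points |

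The documents do not say how often patients start other therapy before progression, so the expected total effect cannot be calculated.

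**The case against.** The strongest reply is that other provisions largely close the window. The patient's end of study is 28 days after the last dose. SAP 5.6.2 schedules tumour assessments only through the EOT visit, which is within 14 days of the last dose. Later contact is survival follow-up, which SAP 5.1 reports separately. With a 4-week confirmation rule, a response that begins on later therapy can hardly be confirmed in time. This stands as far as it goes: it makes the exposure small on the patient-level reading. It does not remove it, because 5.6.2.1 does not say which end of study it means and because confirmation of an earlier response remains exposed.

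The reply is also right on importance. This SAP covers Part A, where response is secondary, safety is primary and no hypothesis test is planned.

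A reader might infer three stronger points that the documents do not support:

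- *That the SAP departs from the protocol on transplant.* The protocol's limit sits in the RECIST appendix. Appendix 8 has no counterpart, so this is a gap shared by both documents.
- *That transplant responses would be credited to CB-103.* Section 5.1.1.1 permits stopping for transplant; it does not presume it. A CR reached before transplant is already a response on CB-103, so transplant can affect only its confirmation and duration.
- *That one response shifts Part B by 10 points in an arm of 10, or 5 in an arm of 20, against the 25% and 40% limits.* Those limits apply to model estimates in Part B, which this SAP does not analyse. Qualifying confirmatory-cohort patients do enter the Part B analyses, but nothing shows that this SAP's BOR rule governs them.

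**Conclusion.** The point holds in limited form. For solid tumours, SAP 5.6.2.1 omits a limit that protocol Appendix 7 states, while SAP section 6 declares no change. For T-ALL/T-LBL the limit is missing from both documents, so confirmation of a remission may follow transplant or other therapy. Any resulting bias is upward. It is small on the patient-level reading of end of study and larger on the study-level or data cut-off reading. The shifts of 16.7 and 2.2 points each rest on one assumed miscounted response and are not estimates of the actual bias.

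A reader might also take the lack of censoring at new therapy for duration of response and PFS as a conflict. It is not: protocol 10.6.2 has no such rule either, and analysing these endpoints that way is a choice.

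One caveat remains. The SAP cites protocol version 4.1, and the version reviewed here is 4.3. The 4.1 wording of Appendix 7 could not be checked.

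**What to change.** In SAP 5.6.2.1:

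- End the BOR window, including the confirming assessment, at the earliest of progression/recurrence, start of new anticancer therapy, death or data cut-off. Make both sentences that define the window agree.
- Apply the same analysis rule to T-ALL/T-LBL, counting transplant as new therapy.
- State that end of study is patient-level.

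A sensitivity analysis of duration of response and PFS censored at new therapy is optional.

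The cost is a few sentences. Protocol 8.2.1 already requires subsequent cancer therapies to be recorded in the eCRF during the safety follow-up. Collection beyond that period is not shown, which is a further reason for the patient-level definition. One consequence should be accepted openly: a remission reached on CB-103 but not confirmed before transplant would no longer count as confirmed. Listing such cases separately keeps them visible.
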